7.1.1 Determination of Sample Size

The sample size will be three cases. This is based on clinical judgment believing this will provided enough data to account for tumor inter-tumor heterogeneity. To assist in addressing tumor heterogeneity three samples from different portions of the tumor will be obtained in each case and their location described in the operative report.

Should a patient fail to be able to take the preoperative Ixazomib dose, undergo the surgery for tumor resection, have useful surgical samples obtained or be unable to reach the postoperative visit for suture/staple removal the patient will be removed from study and a replacement patient will be recruited.

7.1.2 Populations for Analysis

Patients to be enrolled will be have recurrent or progressive glioblastoma for which surgical resection is indicated and have a Karnofsky Performance Status of 60 (ECOG 2) or above.

7.1.3 Procedures for Handling Missing, Unused, and Spurious Data

If there is reason to believe that there is a problem with handling of the tumor specimens likely to render their pharmacokinetic analysis inaccurate the data from this subject will be discarded and a replacement subject recruited. Similarly, if pharmacokinetic or safety data is missing on a subject, and is irretrievable for technical or other reasons, a replacement subject will be recruited.

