2. STUDY OBJECTIVES

2.1 Primary Objectives

1. Measurement of tissue concentration of ixazomib in a glioblastoma after preoperative administration
2. Measurement of blood and plasma concentration of ixazomib during surgical sampling after preoperative administration

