3. STUDY ENDPOINTS

3.1 Primary Endpoints

Determination of brain tumor tissue, blood and plasma concentrations ixazomib

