3.2 Secondary Endpoints

Determination of the safety of MLN9708 after single dose administration in glioblastoma patients undergoing tumor resection

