7.1.5 Pharmacokinetics/Pharmacodynamics/Biomarkers (if applicable)

The primary objective of this study is measurement of tumor tissue concentrations of ixazomib in a glioblastoma after preoperative administration. This will be done in one point in time (during surgery) and from multiple spots in the tumor for each of the three participants. The sample from each site within each tumor will be analyzed separately. These results will allow simple descriptive statistics of the concentration data but no formal pharmacokinetic parameters will be calculated.

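### The tumor-handling rule in Section 7.1.3 discards a whole subject's data, not the faulty specimen, and does not require that decision before the assay result is known

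*Combined protocol and SAP*

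**What the plan says.** Section 7.1.3 has two rules. The first covers a suspected fault in "handling of the tumor specimens likely to render their pharmacokinetic analysis inaccurate the data from this subject will be discarded and a replacement subject recruited". The second reads: "if pharmacokinetic or safety data is missing on a subject, and is irretrievable for technical or other reasons, a replacement subject will be recruited". The first discards and replaces; the second only replaces.

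The surrounding sections show what a subject's data consist of:

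- Tumor: by Section 7.1.1, "three samples from different portions of the tumor will be obtained in each case". By Section 7.1.5, "The sample from each site within each tumor will be analyzed separately". Section 7.1 plans a random-effects model for specimens within patients.
- Blood and plasma: the second primary objective in Section 2.1 is "Measurement of blood and plasma concentration of ixazomib during surgical sampling after preoperative administration". The primary endpoint in Section 3.1 is "Determination of brain tumor tissue, blood and plasma concentrations ixazomib". Section 6.11 schedules three draws per patient, at incision, tumor sampling and closure.
- Safety: the only secondary endpoint, in Section 3.2, is "Determination of the safety of MLN9708 after single dose administration in glioblastoma patients undergoing tumor resection".

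Sections 6.12 and 7.1.1 also replace patients after dosing. In 7.1.1, should a patient "be unable to reach the postoperative visit for suture/staple removal the patient will be removed from study and a replacement patient will be recruited". Section 7.1.2, headed as the analysis populations, restates eligibility and defines no analysis set.

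**The concern.** The trigger in the first rule concerns specimens, but the consequence falls on the subject. Nothing limits the discard to the affected specimen, or to tumor data. A fault in freezing or shipping tumor tissue does not make a blood draw or a postoperative examination unsound, yet the literal wording removes both. Nor does the rule say whether one faulty specimen of three is enough.

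The rule also leaves the decision open. The trigger is a belief that handling was at fault; no criterion, decision-maker or time relative to the assay is given. Section 7.1 makes measurable concentration in tumor the study's question, so the result should not be able to influence which tumor results are set aside. With three patients, a single exclusion carries weight.

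At stake are usable data from a patient who took an investigational drug and had surgery, and a simple protection against selection after the result is seen.

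**Working it through.** The sample size of three rests on clinical judgment (Section 7.1.1), so there is no power figure to reproduce. The check is a count.

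Inputs: 3 patients to be retained (4.2, 7.1.1); 3 tumor specimens per patient (7.1.1); 3 blood draws per patient (6.11; Section 4.1 gives different time points but also three); one safety record per patient. The planned total is 3 × 3 = 9 tumor specimens and 3 × 3 = 9 draws.

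Case: one subject has f faulty tumor specimens (f = 1, 2 or 3), the discard rule is applied, and one replacement is recruited. Four patients are dosed in every row, so the rows differ only in what is kept.

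| Rule applied | Tumor specimens | Blood draws | Safety records |
|---|---|---|---|
| Literal: all of the subject's data discarded | 3 × 3 = 9 | 3 × 3 = 9 | 3 |
| Tumor concentrations only discarded | 3 × 3 = 9 | 4 × 3 = 12 | 4 |
| Only the faulty specimens excluded | 12 − f = 11, 10 or 9 | 4 × 3 = 12 | 4 |

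Compared with specimen-level exclusion, the literal reading gives up:

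- Tumor: (12 − f) − 9 = 2, 1 or 0 sound specimens for f = 1, 2, 3. The losses at f = 1 and f = 2 arise only if fewer than three faulty specimens trigger the rule. At f = 3 no tumor data are gained.
- Blood: 12 − 9 = 3 draws, whatever f is.
- Safety: 4 − 3 = 1 record, whatever f is.

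Under the tumor-only reading, the blood and safety losses vanish and only the 0 to 2 tumor specimens remain.

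Could the analysis use an incomplete patient? Section 7.1.5 analyzes each site on its own, and the Section 7.1 model, with its simple covariance structure, does not need three specimens from every patient. The planned methods therefore do not require whole-subject removal.

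Timing: Section 11.3 lets samples go to the laboratory in one shipment at the end of the study or in several. With one shipment, a site-level handling decision and its replacement would ordinarily precede any result. With several, results on one patient may be back while replacement is still being decided. No passage closes that second route.

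The documents give no mishandling rate, so no probability of triggering the rule is calculated.

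**The case against.** The best case for the plan runs as follows. The trigger speaks of specimens in the plural, and all of a subject's specimens pass through the same weighing, freezing, storage and shipping steps (Section 11.3). The natural case is a shared failure of all three, in which no sound tumor data are lost. Because the trigger concerns tumor handling, the discard can be read as tumor data only; the next sentence names pharmacokinetic and safety data separately, which helps that reading. Replacement restores three patients. All of this is fair, and it limits the size of the point. It does not remove it, because the text states neither limit and on its face says the opposite.

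Three stronger readings are tempting and are not supported.

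- A reader might infer that the plan lets a low concentration be discarded. It does not: the trigger is handling, and nothing authorizes exclusion because of a result. The gap is that nothing prevents relabeling after the fact.
- A reader might attach a bias figure. If any one of four patients could be dropped freely after results, and each had an assumed 50% chance of measurable drug, the chance of showing three of three would rise from 0.5³ = 12.5% to 5 × 0.5⁴ = 31.3%. But the plan has no three-of-three success rule and no such freedom to choose, so this does not describe the trial.
- A reader might infer that adverse events in replaced patients go unreported, or that safety is summarized in completers only. No passage says so. Sections 6.12 and 7.1.1 replace rather than discard, and 6.12 asks for end-of-study procedures at withdrawal. Follow-up to 30 days (4.1), the accrual suspension rule (7.1.7), committee review of serious events (7.1.8) and pharmacovigilance reporting (8.2) do not depend on being retained. What is missing is a sentence naming who is in the safety summary.

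**Conclusion.** The concern holds as a minor one. As written, a tumor-handling fault discards the subject's data without limit to the affected specimen or type of data, and without requiring the decision before the assay result is known. For one affected subject, the literal reading costs 3 blood draws, 1 safety record and 0 to 2 sound tumor specimens relative to specimen-level exclusion; a tumor-only reading costs the 0 to 2 specimens alone. These counts assume one affected subject, one replacement in every scenario and complete sampling otherwise. The tumor loss further assumes that fewer than three faulty specimens are enough.

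The planned dataset does not shrink below three patients, the analysis is descriptive, and safety reporting continues. The undefined safety set is a supporting clarification; it does not show that any dosed patient would be left out.

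**What to change.** In Section 7.1.3:

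- Exclude only the tumor specimen or specimens affected.
- Make the decision from the handling record before the assay result for that specimen is released.
- Keep the subject's other tumor, blood, plasma and safety data in the summaries.
- List each exclusion with its reason.
- State whether a subject with at least one sound tumor specimen is still replaced. The second rule in 7.1.3 and the useful-samples condition in 7.1.1 should agree with the answer. If such a subject is not replaced, three patients are dosed and 9 − 1 = 8 or 9 − 2 = 7 tumor specimens remain; if replaced, four are dosed and 11 or 10 remain. The plan should choose openly.

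As a supporting clarification, state in Section 7.1.2 that the safety summary includes every patient who received ixazomib, replaced or not. Flag those not operated on, because Section 3.2 refers to patients having resection.

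The cost is a wording change with no added procedures. The drawback is that tables may show more than three patients, some with incomplete data.

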7.1.4 Demographic and Baseline Characteristics

The baseline clinical observations will be provided with simple descriptive statistics and tables of observations.

7.1.5 Pharmacokinetics/Pharmacodynamics/Biomarkers (if applicable)

The primary objective of this study is measurement of tumor tissue concentrations of ixazomib in a glioblastoma after preoperative administration. This will be done in one point in time (during surgery) and from multiple spots in the tumor for each of the three participants. The sample from each site within each tumor will be analyzed separately. These results will allow simple descriptive statistics of the concentration data but no formal pharmacokinetic parameters will be calculated.

7.1.6 Safety Analysis

Safety will be assessed with routine postoperative laboratory, vital sign, neurologic exam, and imaging through the day of staple or suture removal. This data will be collected and any adverse events (as defined below) graded and their relationship to the Ixazomib administration determined.

7.1.7 Adverse Event Stopping Rule

For any toxicity \geq one grade above baseline for any pre-existing adverse events (AEs), and any new grade \geq 2 AEs study accrual will be suspended. The study team will review the data to determine the proper course of action. These actions may include further adverse event monitoring and evaluation to assess attribution of the adverse event observed, continued suspension of accrual pending study modification, dose modification, and closure of the trial.

7.1.8 Data Safety Monitoring Plan

Winship Cancer Institute's Data and Safety Monitoring Committee (DSMC) will review toxicity and safety data for each subject following completion of the 2 week post-operative/off-study visit. The sponsor-investigator is responsible for providing adverse event data to the DSMC for review. Should any SAEs occur, from first dose of study drug through 30 days post-administration, the sponsor-investigator will halt enrollment and notify DSMC of event occurrence. Any SAE, regardless of relationship to the study drug, will be reported to the DSMC for review prior to enrollment of subsequent patients to evaluate the safety of trial continuation.

8. ADVERSE EVENTS

8.1 Definitions

8.1.1 Adverse Event Definition

Adverse event (AE) means any untoward medical occurrence in a patient or subject administered a pharmaceutical product; the untoward medical occurrence does not necessarily have a causal relationship with this treatment. An AE can therefore be any unfavorable and unintended sign (including an abnormal laboratory finding), symptom, or disease temporally associated with the use of a medicinal (investigational) product whether or not it is related to the medicinal product. This includes any newly occurring event, or a previous condition that has increased in severity or frequency since the administration of study drug.

An abnormal laboratory value will not be assessed as an AE unless that value leads to discontinuation or delay in treatment, dose modification, therapeutic intervention, or is considered by the investigator to be a clinically significant change from baseline.

8.1.2 Serious Adverse Event Definition

Serious AE (SAE) means any untoward medical occurrence that at any dose:

- Results in **death**.
- Is **life-threatening** (refers to an AE in which the patient was at risk of death at the time of the event. It does not refer to an event which hypothetically might have caused death if it were more severe).
- Requires inpatient **hospitalization or prolongation of an existing hospitalization** (see clarification in the paragraph below on planned hospitalizations).
- Results in **persistent or significant disability or incapacity**. (Disability is defined as a substantial disruption of a person's ability to conduct normal life functions).
- Is a **congenital anomaly/birth defect**.
- Is a **medically important event**. This refers to an AE that may not result in death, be immediately life threatening, or require hospitalization, but may be considered serious when, based on appropriate medical judgment, may jeopardize the patient, require medical or surgical intervention to prevent 1 of the outcomes listed above, or involves

suspected transmission via a medicinal product of an infectious agent. Examples of such medical events include allergic bronchospasm requiring intensive treatment in an emergency room or at home, blood dyscrasias or convulsions that do not result in inpatient hospitalization, or the development of drug dependency or drug abuse; any organism, virus, or infectious particle (eg, prion protein transmitting Transmissible Spongiform Encephalopathy), pathogenic or nonpathogenic, is considered an infectious agent.

Clarification should be made between a serious AE (SAE) and an AE that is considered severe in intensity (Grade 3 or 4), because the terms serious and severe are NOT synonymous. The general term *severe* is often used to describe the intensity (severity) of a specific event; the event itself, however, may be of relatively minor medical significance (such as a Grade 3 headache). This is NOT the same as *serious*, which is based on patient/event outcome or action criteria described above, and is usually associated with events that pose a threat to a patient's life or ability to function. A severe AE (Grade 3 or 4) does not necessarily need to be considered serious. For example, a white blood cell count of 1000/mm³ to less than 2000 is considered Grade 3 (severe) but may not be considered serious. Seriousness (not intensity) serves as a guide for defining regulatory reporting obligations.

8.2 Procedures for Reporting Serious Adverse Events

AEs may be spontaneously reported by the patient and/or in response to an open question from study personnel or revealed by observation, physical examination, or other diagnostic procedures. Any clinically relevant deterioration in laboratory assessments or other clinical finding is considered an AE. When possible, signs and symptoms indicating a common underlying pathology should be noted as one comprehensive event. For serious AEs, the investigator must determine both the intensity of the event and the relationship of the event to study drug administration.

AEs which are serious must be reported to Millennium Pharmacovigilance (or designee) from the first dose of study drug through 30 days after administration of the last dose of ixazomib. Any SAE that occurs at any time after completion of ixazomib treatment or after the designated follow-up period that the sponsor-investigator and/or sub-investigator considers to be related to any study drug must be reported to Millennium Pharmacovigilance (or designee). In addition, new primary malignancies that occur during the follow-up periods must be reported, regardless of causality to study regimen, for a minimum of three years after the last dose of the investigational product, starting from the first dose of study drug. All new cases of primary malignancy must be reported to Millennium Pharmacovigilance (or designee).

Emory University IRB _____
Takeda Oncology Clinical Study Protocol [X16071]

Planned hospital admissions or surgical procedures for an illness or disease that existed before the patient was enrolled in the trial are not to be considered AEs unless the condition deteriorated in an unexpected manner during the trial (e.g., surgery was performed earlier or later than planned). All SAEs should be monitored until they are resolved or are clearly determined to be due to a patient's stable or chronic condition or intercurrent illness(es).

Since this is an investigator-initiated study, the principal investigator, [name], also referred to as the sponsor-investigator, is responsible for reporting serious adverse events (SAEs) to any regulatory agency and to the sponsor- investigator's EC or IRB.

Regardless of expectedness or causality, all SAEs (including serious pretreatment events) must also be reported in English to Millennium Pharmacovigilance (or designee):

Fatal and Life Threatening SAEs within 24 hours of the sponsor-investigator's observation or awareness of the event

All other serious (non-fatal/non life threatening) events within 4 calendar days of the sponsor-investigator's observation or awareness of the event

See below for contact information for the reporting of SAEs to Millennium Pharmacovigilance.

The sponsor-investigator must fax or email the SAE Form per the timelines above. A sample of an SAE Form will be provided.

The SAE report must include at minimum:

- **Event term(s)**
- **Serious criteria**
- **Intensity of the event(s):** Sponsor-investigator's or sub-investigator's determination. Intensity for each SAE, including any lab abnormalities, will be determined by using the NCI CTCAE version 4.0, as a guideline, whenever possible. The criteria are available online at <http://ctep.cancer.gov/reporting/ctc.html>. [25]
- **Causality of the event(s):** Sponsor-investigator's or sub-investigator's determination of the relationship of the event(s) to study drug administration.

Follow-up information on the SAE may be requested by Millennium.

Intensity for each SAE, including any lab abnormalities, will be determined by using the NCI CTCAE version 4.0. The criteria are available online at <http://ctep.cancer.gov/reporting/ctc.html>.

Relationship to all study drugs for each SAE will be determined by the investigator by responding yes or no to the question: Is there a reasonable possibility that the AE is associated with the study drug(s)?

Sponsor-investigator must also provide Millennium Pharmacovigilance with a copy of all communications with applicable regulatory authorities related to the study product(s), as soon as possible but no later than 4 calendar days of such communication.

SAE and Pregnancy Reporting Contact Information

[contact]
Email: [contact]

Suggested Reporting Form:

- SAE Report Form (provided by Millennium)
- US FDA MedWatch 3500A:
<http://www.fda.gov/Safety/MedWatch/HowToReport/DownloadForms/default.htm>
- Any other form deemed appropriate by the sponsor-investigator

8.3 Procedures for Reporting Drug Exposure During Pregnancy and Birth Events

If a woman becomes pregnant or suspects that she is pregnant while participating in this study or within 90 days after the last dose, she must inform the investigator immediately and permanently discontinue study drug. The sponsor-investigator must immediately fax a completed Pregnancy Form to the Millennium Department of Pharmacovigilance or designee (see Section 8.2). The pregnancy must be followed for the final pregnancy outcome.

If a female partner of a male patient becomes pregnant during the male patient's participation in this study, the sponsor-investigator must also immediately fax a completed Pregnancy Form to the Millennium Department of Pharmacovigilance or designee (see Section 8.2). Every effort should be made to follow the pregnancy for the final pregnancy outcome.

Suggested Pregnancy Reporting Form:

- Pregnancy Report Form (provided by Millennium)

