4.2 Number of Patients

Three patients will be enrolled in this study. Enrollment will commence at the time of Ixazomib administration.

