4.3 Duration of Study

This investigation will enroll approximately 1 patient every 2 months with completion expected 6 months after Winship Cancer Center checklists are completed. For the individuals enrolled, study activity will last from the day of surgery until the day the sutures or staples are removed. The average time period for the wound to heal well enough for suture or staple removal is 10-17 days depending on the nature of the surgical wound. (please note that all serious adverse events must be reported up to 30 days after the dose of ixazomib as described in Section 8.2: Procedures for Reporting Serious Adverse Events). The subject will continue to follow-up with their surgeon and oncologist as per standard care for their circumstance and therapy dictates and the adverse events will be captured at those follow-up visits.

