5. STUDY POPULATION

5.1 Inclusion Criteria

Each patient must meet all of the following inclusion criteria to be enrolled in the study:

1. Male or female patients 18 years or older.
2. Voluntary written consent must be given before performance of any study related procedure not part of standard medical care, with the understanding that consent may be withdrawn by the patient at any time without prejudice to future medical care.
3. Female patients who:
 - Are postmenopausal for at least 1 year before the screening visit, OR
 - Are surgically sterile, OR
 - If they are of childbearing potential, agree to practice 2 effective methods of contraception, at the same time, from the time of signing the informed consent form through 90 days after the last dose of study drug, OR
 - Agree to practice true abstinence when this is in line with the preferred and usual

lifestyle of the subject. (Periodic abstinence [eg, calendar, ovulation, symptothermal, post-ovulation methods] and withdrawal are not acceptable methods of contraception.)

Male patients, even if surgically sterilized (ie, status post-vasectomy), must agree to one of the following:

- Agree to practice effective barrier contraception during the entire study treatment period and through 90 days after the last dose of study drug, OR
 - Agree to practice true abstinence when this is in line with the preferred and usual lifestyle of the subject. (Periodic abstinence (eg, calendar, ovulation, symptothermal, post-ovulation methods] and withdrawal are not acceptable methods of contraception.)
4. Patients must have a previous diagnosis of a recurrent or progressive glioblastoma for which surgical resection is now indicated.
 5. Eastern Cooperative Oncology Group (ECOG) performance status and/or other performance status 0, 1, or 2 or (Karnofsky Performance Status of 60 or above).
 6. Patients must meet the following clinical laboratory criteria:
 - Absolute neutrophil count (ANC) $\geq 1,500/\text{mm}^3$ and platelet count $\geq 100,000/\text{mm}^3$. Platelet transfusions to help patients meet eligibility criteria are not allowed within 3 days before study enrollment.
 - Hemoglobin > 9 g/dL
 - Total bilirubin $\leq 1.5 \times$ the upper limit of the normal range (ULN).
 - Alanine aminotransferase (ALT) and aspartate aminotransferase (AST) $\leq 3 \times$ ULN for the lab utilized.
 - Creatinine ≤ 1.5 mg/dL
 - Calculated creatinine clearance ≥ 30 mL/min (see Section 11.2).

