6.2 Study Drug Administration

Ixazomib Administration

All protocol-specific criteria for administration of study drug must be met and documented before drug administration. Study drug will be administered or dispensed only to eligible patients under the supervision of the investigator or identified subinvestigator(s). Patients should be monitored for toxicity, as necessary, and doses of ixazomib should be modified as needed to accommodate patient tolerance to treatment; this may include symptomatic treatment, dose interruptions, and adjustments of ixazomib dose (see Section 6.3).

Capsules of ixazomib will also be referred to as study drug. Study drug will be supplied by Millennium as capsules of 0.2-, 0.5-, and 2.0 mg, or as capsules of 2.3-, 3.0- and 4.0 mg ixazomib.

The prescribed administration of the ixazomib dose in this study is one 4.0 mg dose approximately 3 hours prior to surgery. No further doses of ixazomib will be administered. The dose will be dispensed by the Emory University Hospital Research Pharmacy and administered by the PI who will document the time of administration, the dose, and toleration of the dose in the operative dictation. The patient will be in the preoperative waiting room and then the preoperative holding area after administration while being prepared for surgery. As there is only one dose used in this study, and it will be documented as part of the surgical procedure, no drug diary will be used.

Patients will be instructed to swallow ixazomib capsules whole, with water, and not to break, chew, or open the capsules. Study drug should be taken on an empty stomach (no food or drink) as they will have been NPO since midnight on the day surgery in preparation for general anesthesia. Each capsule should be swallowed separately with a sip of water. A total of approximately 8 ounces (240 mL) of water should be taken with the capsules.

Ixazomib Destruction

Investigational ixazomib (expired or end of study) should be destroyed on site according to the institution's standard operating procedure. Be sure to document removal and destruction on drug accountability logs.

Anesthetic agents, corticosteroids, anticonvulsants, antibiotics and other supportive agents will be administered during and after the surgical procedure (respecting those not allowed in the exclusion criteria list item number 8 above).

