6.5 Precautions and Restrictions

- Fluid deficit should be corrected before initiation of treatment and during treatment with ixazomib.

Pregnancy

It is not known what effects ixazomib has on human pregnancy or development of the embryo or fetus. Therefore, female patients participating in this study should avoid becoming pregnant, and male patients should avoid impregnating a female partner. Nonsterilized female patients of

reproductive age group and male patients should use effective methods of contraception through defined periods during and after study treatment as specified below.

Female patients must meet 1 of the following:

- Postmenopausal for at least 1 year before the screening visit, or
- Surgically sterile, or
- If they are of childbearing potential, agree to practice 2 effective methods of contraception from the time of signing of the informed consent form through 90 days after the last dose of study drug, or
- Agree to practice true abstinence, when this is in line with the preferred and usual lifestyle of the subject. (Periodic abstinence [eg, calendar, ovulation, symptothermal, postovulation methods] and withdrawal are not acceptable methods of contraception.)

Male patients, even if surgically sterilized (ie, status postvasectomy) must agree to 1 of the following:

- Practice effective barrier contraception during the entire study treatment period and through 90 days after the last dose of study drug, or
- Agree to practice true abstinence, when this is in line with the preferred and usual lifestyle of the subject. (Periodic abstinence [eg, calendar, ovulation, symptothermal, postovulation methods for the female partner] and withdrawal are not acceptable methods of contraception.)

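### Section 8.3 requires reporting of a partner pregnancy only during the male patient's participation, leaving about 60 to 80 of the 90 days after the dose without a reporting duty

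*Combined protocol and SAP*

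**What the plan says.** Section 8.3 contains two pregnancy-reporting rules in adjacent paragraphs.

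- Female patients: the rule applies if she becomes pregnant, or suspects it, "while participating in this study or within 90 days after the last dose, she must inform the investigator immediately". The sponsor-investigator then sends a Pregnancy Form, and the pregnancy has to be followed to its outcome.
- Partners of male patients: the form is required "If a female partner of a male patient becomes pregnant during the male patient's participation in this study". No period after the dose is given, and nobody is named as having to tell the investigator.

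The contraception rules for men run longer. Section 5.1 offers a man two options: "Agree to practice effective barrier contraception during the entire study treatment period and through 90 days after the last dose of study drug", or true abstinence. Section 6.5 repeats this: "Practice effective barrier contraception during the entire study treatment period and through 90 days after the last dose of study drug", or abstinence. Section 6.5 gives the reason: the drug's effects on human pregnancy and on the embryo or fetus are unknown.

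Participation is short. Section 4.2 states "Enrollment will commence at the time of Ixazomib administration", and Section 6.2 states "No further doses of ixazomib will be administered". Section 4.3 says "study activity will last from the day of surgery until the day the sutures or staples are removed", and Section 4.1 puts the patient off study at the postoperative clinic visit.

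**The concern.** The protocol uses one 90-day period for prevention in both sexes, but for reporting it uses that period only for women. Followed as written, Section 8.3 creates no duty to report or follow a conception that occurs after a male patient's last study visit but while he is still under the contraception requirement. No section explains the difference.

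What is at stake is the completeness of safety reporting for a partner and fetus, for a drug whose effects on pregnancy the protocol calls unknown. The tumor, blood and plasma concentration results do not depend on it.

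**Working it through.** The plan gives no figure of its own for this gap, so there is none to reproduce. The check is interval arithmetic plus a search for any other rule that would cover the missing days.

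**Inputs**

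- Day 0 is the day of the only dose, which is also the day of surgery (Sections 4.1 and 6.2).
- The contraception period for men ends on day 90 (Sections 5.1 and 6.5).
- Participation ends at suture or staple removal: 10 to 20 days after surgery in the Schedule of Events (Section 6.11), 10 to 17 days on average in Section 4.3, and about two weeks in the Protocol Summary.
- The alternative end is day 30, if participation is read as the adverse event reporting period (Section 4.1).

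**Formula.** With participation ending on day D, days without a reporting duty = 90 − D, and share = (90 − D) / 90.

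| End of participation | D | Days without a duty | Share of 90 days |
|---|---|---|---|
| Earliest removal in the schedule | 10 | 90 − 10 = 80 | 88.9% |
| About two weeks | 14 | 90 − 14 = 76 | 84.4% |
| Upper end of the average in Section 4.3 | 17 | 90 − 17 = 73 | 81.1% |
| Latest removal in the schedule | 20 | 90 − 20 = 70 | 77.8% |
| 30-day adverse event period | 30 | 90 − 30 = 60 | 66.7% |

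With the female-patient window applied to partners, the gap is 90 − 90 = 0 days.

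**Does another rule cover these days?**

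- Section 8.1.2 does not list pregnancy as a seriousness criterion. It does list a birth defect, but Section 8.1.1 defines an adverse event as an occurrence in the person given the product, and the partner was not given it.
- Section 8.2 requires all serious events to be reported for 30 days after the dose. After that, apart from new primary malignancies, reporting depends on a judgment that the event is drug-related. At most this could pick up a bad outcome that somebody happens to hear of. It does not start follow-up of a pregnancy.
- Capture of adverse events at later standard-care visits (Sections 4.1, 4.3 and 6.11) concerns the patient's own events.

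None of these rules closes the gap.

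**The case against.** The best case on the other side has five parts.

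**Participation is undefined.** The 10-to-20-day end point is inferred from the off-study wording, and some obligations run on: adverse events for 30 days, new primary malignancies for at least three years (Section 8.2). The first part of this stands, and it is why the gap is given as a range reaching down to 60 days. A three-year reading would remove the gap, but it is hard to sustain. Section 4.1 says when the patient is off study, and the female-patient sentence in 8.3 adds 90 days to participation, which would be redundant if participation already lasted that long.

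**The 90 days for men is a contraception period.** This stands. A reader might infer that the protocol declares a 90-day exposure or risk window for men and then contradicts it. The documents do not go that far. They set a contraception requirement, say that effects on pregnancy are unknown, and nowhere say that partner reporting must match it. This is a failure of alignment, not a direct contradiction.

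**A reader might also infer that later partner pregnancies would go unreported.** The text supports only that they need not be reported. Nothing bars a voluntary report.

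**The difference may be deliberate.** A partner is not a trial subject, and 8.3 also asks only for every effort to follow her pregnancy, where for a female patient follow-up is mandatory. A softer follow-up duty is understandable. It does not explain a shorter reporting window, and the protocol offers no reason for one.

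**The event is unlikely.** Contraception or abstinence is already required, and three patients are planned, plus any replacements. This stands, and it keeps the point minor.

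**Conclusion.** The point holds as a minor inconsistency in safety reporting. Section 8.3 requires a partner-pregnancy report only during the man's participation, while the same section uses 90 days after the last dose for female patients, and Sections 5.1 and 6.5 use 90 days for contraception in men. About 60 to 80 of the 90 days (67% to 89%) carry no requirement to report or follow a partner pregnancy.

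The range rests on two assumptions: that the single dose marks day 0, and that participation ends between the off-study visit (day 10 to 20) and the end of adverse event reporting (day 30). On each of these readings most of the period is uncovered. The chance of an event in this trial is low, and neither the concentration endpoint nor its analysis is affected.

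**What to change.** Reconcile Section 8.3 with Sections 5.1 and 6.5. Give the partner-pregnancy sentence the window that 8.3 already uses for female patients: "while participating in this study or within 90 days after the last dose".

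Add one sentence saying that the male patient is to inform the investigator if his partner becomes pregnant in that period. The longer window alone would not be enough, because no study visit falls after suture removal and the partner paragraph names nobody as responsible for passing on the information. The consent pages are not in the copy reviewed, so whether patients are already told this could not be checked; the consent text should agree with the revised section.

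The cost is one phrase and one sentence. No visit, sample or analysis is added, and with three patients the burden is negligible.
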